6.5 Sponsor Responsibility for Reporting Adverse Events

All Adverse Events will be reported to regulatory authorities, IRB/IECs and investigators in accordance with all applicable global laws and regulations.

7. AGENT INFORMATION

7.1 Investigational Product: Pembrolizumab

Pembrolizumab is a potent humanized IgG4 mAb with high specificity of binding to the PD-1 receptor, thus inhibiting its interaction with PD-L1 and PD-L2. Based on preclinical in vitro data, pembrolizumab has high affinity and potent receptor blocking activity for PD-1. Pembrolizumab has an acceptable preclinical safety profile and is being advanced for clinical development as an IV immunotherapy for advanced malignancies.

Additional detailed information on pembrolizumab is available in the Investigator's Brochure.

The investigator shall take responsibility for and shall take all steps to maintain appropriate records and ensure appropriate supply, storage, handling, distribution and usage of investigational product in accordance with the protocol and any applicable laws and regulations.

7.1.1 Description

Pembrolizumab is a humanized anti-PD-1 mAb of the IgG4/kappa isotype with a stabilizing S228P sequence alteration in the fragment crystallizable (Fc) region. Pembrolizumab binds to human PD-1 and blocks the interaction between PD-1 and its ligands. The theoretical molecular weight of the polypeptide is 146,288 Da and its theoretical pI is 7.5. Pembrolizumab exhibits linear pharmacokinetics at dose levels of clinical relevance (1-10 mg/kg). It exhibits low clearance and limited volume of distribution that is typical for therapeutic antibodies. Mean estimated t_{1/2} values are 14.1-21.6 days. Additional information on pembrolizumab nomenclature is detailed in the following table:

Code Name	Pembrolizumab (anti-PD-1)
Other Code Name	SCH 900475 (anti-PD-1) MK-3475
Chemical Name	Humanized X PD-1 mAb (H409A11) IgG4
CAS Number	1374853-91-4
CAS Name	Anti-(human protein PDCD1 (programmed cell death 1)) immunoglobulin G4 (human-Mus musculus monoclonal heavy chain) disulfide with human-Mus musculus monoclonal light chain, dimer
Generic Name	Pembrolizumab
Commercial Name	Keytruda®

7.1.2 Form

Pembrolizumab is supplied as a clear to opalescent solution that is essentially free of extraneous particles and may contain proteinaceous particulates. One dosage form of pembrolizumab will be provided by Merck in Type I glass vials intended for single use only as summarized in the following table:

Product Name & Potency	Dosage Form
Pembrolizumab 100 mg/ 4mL	Solution for Infusion

Pembrolizumab solution for infusion is a sterile, non-pyrogenic, aqueous, preservative-free solution. Pembrolizumab solution for infusion contains an excess fill of 6.25 mg (equivalent to 0.25 mL solution) to ensure the recovery of label claim of 100 mg pembrolizumab per vial (equivalent to 4.0 mL of solution).

7.1.3 Packaging and Labeling Information

Clinical supplies will be affixed with a clinical label in accordance with regulatory requirements. Vials will be provided in an open label fashion for subject dosing.

7.1.4 Clinical Supplies Disclosure

This trial is open-label; therefore, the subject, the trial site personnel, the Sponsor and/or designee are not blinded to treatment. Drug identity (name, strength) is included in the label text; random code/disclosure envelopes or lists are not provided.

7.1.5 Storage, Handling and Preparation Requirements

As specified in the Pharmacy Manual for pembrolizumab as provided by the Sponsor.

7.1.6 Administration

Pembrolizumab will be administered as a 30-minute IV infusion using an infusion pump (treatment cycle intervals may be increased due to toxicity as described in Section 6.2). Sites should make every effort to target infusion timing to be as close to 30 minutes as possible. However, given the variability of infusion pumps from site to site, a window of -5 minutes and +10 minutes is permitted (i.e., infusion time is 30 minutes: -5 min/+10 min). Attach the infusion line to the pump and prime the line, either with normal saline (at least 25 mL) or with infusion solution as per local SOP, before starting the infusion. Maximum infusion rate should not exceed 6.7 ml/min through a peripheral or indwelling catheter. Use 30 mL normal saline to flush the infusion line at the end of the infusion if institutional guidelines allow.

Unused infusion solution should not be used for another infusion of the same participant or different participant.

DO NOT administer the product as an intravenous push or bolus.

DO NOT combine, dilute or administer it as an infusion with other medicinal products.

A central line is not required for pembrolizumab administration, but may be used if available.

The following infusion set materials are compatible with pembrolizumab

- PVC infusion set that is plasticized using Di-2-ethylhexyl Terephthalate DEHP
- PVC and tri-(2-ethylhexyl) trimellitate (TOTM) infusion set
- Polyethylene lined PVC infusion set
- Polyrethane
- Plybutadiene

A sterile, non-pyrogenic, low-protein binding 0.2 to 5 μ m in-line filter made of polyethersulfone (PES) or polysulfone must be used during administration to remove any adventitious particles. If the infusion set does not contain a 0.2 to 5 μ m in-line filter, it is recommended to use a 0.2 to 5 μ m add-on filter which may contain an extension line (the materials of the extension line and filter should be as mentioned above).

7.1.7 Ordering

Investigative sites will order and acquire Pembrolizumab directly from Merck per Appendix B Section 4.0 (Data and Safety Monitoring Plan).

7.1.8 Accountability

The investigator is responsible for keeping accurate records of the clinical supplies received from Merck or designee, the amount dispensed to and returned by the subjects and the amount remaining at the conclusion of the trial.

7.1.9 Destruction and Return

Upon completion or termination of the study, all unused and/or partially used investigational product will be destroyed at the site per institutional policy. It is the Investigator's responsibility to arrange for disposal of all empty containers, provided that procedures for proper disposal have been established according to applicable federal, state, local and institutional guidelines and procedures, and provided that appropriate records of disposal are kept.

8. BIOMARKER STUDIES

The precise mechanism by which Pembrolizumab exerts anti-tumor activity is not clear but it is likely related to modulation of the immune system to generate anti-tumor immune responses that are capable of eliminating existing tumors and generating immune memory responses to prevent future relapse. The effect of PD-1 blockade on effector T cells and regulatory T cells is a critical component of anti-tumor activity. The current study will explore baseline levels as well as changes following pembrolizumab administration for association with outcome. In addition, archival tumor expression of PD-L1 will also be evaluated. Peripheral blood will be collected prior to initiation of study therapy, prior to surgery and periodically during the study. Archival tumor will also be collected on all patients. Since this is a surgery study, all tumor samples obtained during the study will be used to evaluate effect of therapy. In addition, if a biopsy or surgical resection is performed at the time of potential progression, a tumor sample (block or slides) should also be submitted if sufficient tumor material is available.

Evaluation of correlative immunologic biomarkers will be performed at the Brain Tumor Immunology Research Laboratory, UCLA Jonsson Comprehensive Cancer Center. Instructions for sample processing and shipping are provided in this section.

Please note that submitting institution is responsible for the costs of shipping and handling.

8.1 Immunophenotyping

The absolute lymphocyte count and proportion of specific lymphocyte subsets will be quantified at each time point. Using fluorescence activated cell sorting (FACS) analysis, lymphocyte/leukocyte subsets, activation markers, and negative costimulatory molecules will be evaluated before and after administration of pembrolizumab. The CD4/CD8 ratio, Treg populations (CD3+CD4+CD25+CD127low), activation (CD3+CD8+CD25/69), MDSC (CD33+HLA-DrlowCD11b+PD-L1+), negative costimulatory markers (CD3+CD4/8+PD-1+, CD3+CD4/8+CTLA-4+) will be determined at each time point. FACS analysis will be performed on PBMC obtained from Ficoll density gradient separation of whole blood. Blood draws for this testing will be done pre treatment, pre-surgery, and with every MRI scan done for tumor status. Guidance on peripheral blood collection, processing and shipping is provided in Table 6 below.

8.2 TIL Density and TCR Overlap

In this study we plan to evaluate whether next generation sequencing of the T cell receptor (TCR) repertoire within GBM and blood can identify shared TCRs, which can then effectively track anti-tumor immune responses induced by PD-1 mAb blockade. Genomic DNA will be isolated from fresh-frozen tumor (protocol surgery) and peripheral blood (immune monitoring timepoints) and subjected to next generation sequencing through the TCRV β region to quantify TIL density and assess the overlap between tumor and peripheral blood. The TIL density and TCR overlap will then be correlated with clinical variables to identify potential biomarkers with prognostic and predictive value for outcomes (ORR, PFS, OS and toxicity). The TIL density and TCR overlap will be performed at Adaptive Biotechnologies (Seattle, WA). Investigators at the UCLA Brain Tumor Immunology Research Laboratory will perform analysis. Guidance on peripheral blood

collection, processing and shipping is provided in Table 6 below.

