5. TREATMENT PLAN

This is a pilot surgical trial to evaluate early immunologic pharmacodynamic parameters for the PD-1 checkpoint inhibitor, pembrolizumab (MK-3475), in patients with surgically accessible recurrent/progressive glioblastoma. The principle goal of this study is to understand, in surgically resectable recurrent/progressive GBM, if neoadjuvant pembrolizumab elicits a systemic immunologic response, a tumoral immunologic response and toxicity and if that response can be correlated with other non-invasive measures of pembrolizumab bioactivity (tumor, blood, imaging, and clinical outcomes). The study includes 2 stages, in the first stage (**Stage 1**), for optimal understanding of the effect of the drug on tumor tissue patients will be randomized in to Group A or Group B. In the second stage (**Stage 2**), additional patients will be enrolled to an expansion arm of Group A only to specifically study the effect of the drug on cell cycle/cancer proliferation related genetic signature.

Stage 1:

Groups A and B: Patients will be randomly assigned to either group A or B with a 1:1 randomization ratio prior to surgery. Patients in all groups will receive the study drug pembrolizumab after tumor resection. Only Group A will receive a single infusion of pembrolizumab of 200mg 14± 5 days prior to surgery (when scheduling, please keep in mind that the two pre-surgical plasma samples should be drawn greater than 10 days apart - see Table 6 for full details). Group B will not receive study drug prior to surgery. **This randomization scheme should not negatively impact study accrual and will provide an invaluable control cohort for PD evaluations.**

Group A: Neoadjuvant/adjuvant evaluation: Fifteen eligible patients will receive a single infusion of pembrolizumab of 200mg 14± 5 days prior to scheduled surgical resection for

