Group B: adjuvant evaluation: Fifteen eligible patients will not receive study drug prior to scheduled surgical resection for recurrent/progressive glioblastoma. The two required pre-surgical plasma samples should be drawn greater than 10 days apart - see Table 6 for full details). Tumor samples will be obtained at time of surgery. The tissue from this surgery (fresh, frozen and FFPE) and the archived tissue from the most recent surgery prior to registration revealing glioblastoma (FFPE) will be processed so as to best achieve the primary, secondary and exploratory PD objectives. After recovery from surgery (once participant has recovered from surgery, but no more than 35 days following surgery), patients will begin Q 3 week pembrolizumab at 200mg IV until tumor progression or adverse event requiring discontinuation of study drug. Blood samples will be obtained as pharmacodynamic markers throughout the study. Dose decreases and symptomatic management will occur based upon preset adverse event determination. DLTs will not be determined. The toxicity evaluation period will begin with registration and extend to 30 days after last treatment day. Patients will be followed for MRI changes, clinical exam and steroid doses from the registration period and extend to the second progression. After second progression, patients will be followed every 3 months for vital status until death.

Stage 2:

Group A expansion only: For this stage of the study, 25 additional patients will be enrolled to Group A only with a goal of 20 evaluable patients.

Expansion of Group A: Neoadjuvant/adjuvant evaluation: An additional 20-25 patients will receive a single infusion of pembrolizumab of 200mg 14± 5 days prior to scheduled surgical resection for recurrent/progressive glioblastoma (when scheduling, please keep in mind that the two pre-surgical plasma samples should be drawn greater than 10 days apart - see Table 6 for full details). Tumor samples will be obtained at time of surgery. The tissue from this surgery (fresh, frozen and FFPE) and the archived tissue from the archived tissue from the most recent surgery prior to registration revealing glioblastoma (FFPE) will be processed so as to best achieve the primary, secondary and exploratory PD objectives. After recovery from surgery (once participant has recovered from surgery, but no more than 35 days following surgery), patients will resume Q 3 week pembrolizumab at 200mg IV until tumor progression or adverse

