8.4 Gene expression signatures and somatic mutations

Tumor samples from the protocol surgery should be immersed in Allprotect tissue reagent solution (Qiagen) or RNA-later® reagent and shipped to the UCLA Brain Tumor Research Laboratory. RNA Seq will be performed at the UCLA GenoSeq Core facility and analyzed. We will assess the number of somatic mutations in each tumor and this data will be correlated with clinical variables to identify potential biomarkers with prognostic and predictive value for outcomes (ORR, PFS, OS). We will also develop immune signatures with the sequencing data and evaluate whether the presence of a pre-existing immune signature can also be correlated with clinical variables.

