12.2.3 Power and Sample Size for primary endpoint

Stage 1:

Group B is an independent concurrent control to evaluate TIL density in Group A due to the infeasibility of multiple resections within a short time period for patients with recurrent GBM. Patients will be randomly assigned to either group A or B with a 1:1 randomization ratio prior to surgery. Based on our preliminary data, the mean of TIL density is estimated to be 0.4 (T cell per nucleating) (SD = 0.5) in the control group (Group B). Fifteen patients per group (total of 30 evaluable) achieve 85% power to detect an increase of 0.5 of TIL density comparing Group A versus Group B at an alpha level of 0.05 (1-sided) using a two-sample t-test.

Stage 2:

An extension based on interim data has the primary scientific endpoint of evaluating the cell cycle signature in patients receiving neoadjuvant pembrolizumab. This extension will aim to enroll 25 additional patients with a goal of 20 evaluable patients to Group A. Group B is an independent

concurrent control to evaluate the cell cycle-related gene signature in Group A. Based on the preliminary data, the mean tumor cell cycle-related gene expression signature is estimated to be -0.3 for neoadjuvant pembrolizumab (SD=0.66) and +0.37 for control (SD=0.64), which corresponds to an effect size of 1.1. With the addition of 20 more patients in Group A, the one-sided two-sample T-test (alpha level: 0.05) will have 81.73% power to detect an effect size of 1.1 for the difference of tumor cell cycle-related gene expression signature between the two groups.

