12.2.6.3 Statistical Methods for Exploratory Analyses

Variables involved in exploratory analyses will be examined graphically and summarized by descriptive statistics. Data transformation may be applied to quantitative variables prior to analyses if deemed necessary.

Bivariate association analyses will be conducted to evaluate the associations between exploratory biomarkers and clinical outcomes and adverse events for the objectives listed in 1.4. The analyses will be performed for each group separately and/or combined as deemed appropriate. Specifically, Pearson or Kendall's tau correlation coefficients will be calculated to evaluate the association between quantitative variables, Chi-squared tests or Fisher's exact tests will be used to examine the association between categorical or ordinal variables, and ANOVA will be performed to study the association between a quantitative variable and a categorical variable. The association between biomarkers and clinical outcomes (PFS and OS) will be evaluated using Cox regression. For markers with multiple measurements over time, data at a specific time point or change from pre-treatment will be used in the above bivariate analyses as deemed appropriate.

Changes in markers pre- and post-treatment will be assessed using paired t-tests.

Between-group comparisons will be conducted for PFS, OS, and PD-1, PDL-1 IHC expression. Survival analyses via Kaplan-Meier curves and log-rank tests will be used to estimate and compare PFS, second PFS, and OS between Group A and Group B. PD-1 and PDL-1 IHC expression will be compared between Groups A and B using two-sample t-tests.

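### The planned one-marker tests in patients who all receive pembrolizumab cannot separate predictive from prognostic biomarkers, so the predictive aim in 8.2 and 8.4 has no analysis behind it

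*Combined protocol and SAP*

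**What the plan says.** Section 8.2 states that TIL density and TCR overlap will be "correlated with clinical variables to identify potential biomarkers with prognostic and predictive value for outcomes (ORR, PFS, OS and toxicity". Section 8.4 says of the somatic mutation count that "this data will be correlated with clinical variables to identify potential biomarkers with prognostic and predictive value for outcomes (ORR, PFS, OS".

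The methods are in 12.2.6.3. They are bivariate: Pearson or Kendall correlation, chi-squared or Fisher tests, ANOVA, and for time-to-event outcomes "The association between biomarkers and clinical outcomes (PFS and OS) will be evaluated using Cox regression". The groups may be analysed apart, together, or both, at the analyst's discretion. No marker-by-treatment term is mentioned, and the plan does not say what would make a marker prognostic or predictive.

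On treatment, Section 5 says "Patients in all groups will receive the study drug pembrolizumab after tumor resection". The one randomised contrast is the single pre-surgical dose: "Patients will be randomly assigned to either group A or B with a 1:1 randomization ratio prior to surgery" (12.2.3). It exists only in Stage 1, because in Stage 2 "additional patients will be enrolled to an expansion arm of Group A only" (Section 5).

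The governing objective (1.4.1) is exploratory and speaks of associations between markers and outcomes. The introduction to Section 8 also speaks of association with outcome.

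**The concern.** A prognostic marker relates to outcome whatever the treatment. A predictive marker changes the size of the treatment effect, so showing it needs outcomes with and without the treatment at different marker levels. This trial has no arm without pembrolizumab after surgery, and the planned tests do not compare treatments at all. The predictive half of the aim therefore has no analysis that could support it.

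There is a second difficulty with the markers named. TIL density, TCR overlap and somatic mutations are measured on tumour from the protocol surgery. In Group A that tissue follows the first dose; in Group B it precedes any dose. If the groups are pooled, marker level is mixed with treatment group.

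At stake is what the trial may say about its biomarkers. An association found in about 50 treated patients could be reported, in the protocol's own words, as having predictive value.

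**Working it through.** **1. Identification.** Let T = 1 for any pembrolizumab and m = the marker. The hazard is

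h(t) = h0(t) · exp(βm + τT + γmT),

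where β is the prognostic part and γ the predictive part. Section 5 sets T = 1 for everyone, so the model reduces to a one-marker Cox model with coefficient β + γ. The pairs (β, γ) = (log 2, 0) and (0, log 2) give the same likelihood. No analysis in 12.2.6.3 can tell them apart, at any sample size.

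**2. What the design can identify.** Let D = 1 for the pre-surgical dose. A term δmD is estimable by comparing A with B. It is protected by randomisation only in Stage 1, and is interpretable only if m was measured before D was given. Archived tissue (8.3, Table 6) and pre-treatment blood (Table 6) qualify. Tumour taken at the protocol surgery does not.

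**3. How the planned test behaves.** The plan states no power or error rate for these analyses, so there is no figure to reproduce. As a check on the design inputs, the Stage 1 primary power (15 v 15, difference 0.5, SD 0.5, one-sided 0.05, t-test) comes to 84.8% against the stated 85%.

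Inputs from the documents: 15 v 15 (Stage 1); 35 v 15 (with 20 more in Group A); A v B overall survival hazard ratio 0.39 (1.1); two-sided 0.05 (12.2.6). Assumed: exponential times, 80% of patients with an event, a marker independent of group, and the marker hazard ratios shown. There were 4,000 simulated trials per row.

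| Sizes (A v B) | HR per SD in A / in B | One-marker Cox, p<0.05 | Marker-by-group term, p<0.05 |
|---|---|---|---|
| 15 v 15 | 1.0 / 1.0 | 5.2% | 6.7% |
| 15 v 15 | 1.5 / 1.5 | 37.6% | 6.5% |
| 15 v 15 | 2.0 / 2.0 | 77.0% | 6.3% |
| 15 v 15 | 2.0 / 1.0 | 29.2% | 32.8% |
| 35 v 15 | 1.0 / 1.0 | 5.3% | 6.2% |
| 35 v 15 | 1.5 / 1.5 | 60.2% | 6.2% |
| 35 v 15 | 2.0 / 2.0 | 95.0% | 5.4% |
| 35 v 15 | 2.0 / 1.0 | 77.1% | 48.3% |

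Rows with equal hazard ratios have no modification by the pre-surgical dose. The one-marker test responds to them, as it should for an association; the marker-by-group test stays near its nominal 5%. A second set of assumptions (A v B hazard ratio 0.6, about 70% events, protective marker at 0.7, 0.6 and 0.5 per SD) gives one-marker rates of 32%, 56% and 79% with 15 v 15, and 50%, 78% and 96% with 35 v 15. A weaker marker gives much less: at 0.85 per SD, 13% and 16%.

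**4. The timing of the tissue.** Take a marker with no relation to outcome within either group, but raised by 1 SD in Group A. This is the Stage 1 planning effect in 12.2.3: 0.5 / 0.5 = 1. With the A v B hazard ratio of 0.39, the pooled one-marker test reaches p<0.05 in about 14% to 18% of trials, depending on group sizes and censoring. With group in the model the rate is about 6%. If the A v B hazard ratio is 0.6, the pooled rate is about 7% to 9%.

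**The case against.** The strongest reply is that this is two sentences of assay description, not a flaw in the analysis. Objective 1.4.1, the introduction to Section 8 and 12.2.6.3 all speak of association, and association tests are right for that. Sections 8.2 and 8.4 speak of potential biomarkers and name both properties together; no rule turns a small p-value into a predictive label. The phrase could also carry its everyday sense of forecasting an outcome. Section 12.2.6.3 allows analysis by group, which gives group-specific estimates.

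Most of this stands, and it limits the point. A reader might infer that a prognostic marker will be labelled predictive. The documents do not say so; they leave the two indistinguishable. A reader might also take the 32% to 96% rates as false-positive rates. They are the power to detect a real association under assumed effects, and would be errors only if every detection were called predictive. Nor do the tests detect prognosis alone: they detect prognosis and effect modification combined.

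What does not stand is that nothing needs changing. Separate group estimates are not a test of their difference, and the stated aim still includes a property that the plan cannot assess.

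**Conclusion.** The concern holds as a limit on what may be concluded. With every patient treated and only bivariate tests planned, the trial cannot show that any biomarker is predictive for pembrolizumab. This follows from the design and needs no assumed numbers. The simulations show only that the one-marker test responds to prognosis. Their rates rest on assumed marker effects, event fractions and, in part, the interim hazard ratio of 0.39.

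It would go too far the other way to call these associations purely prognostic. That label is equally unsupported when everyone is treated, and more so for TIL density measured after dosing in Group A.

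Severity is minor. The analyses are exploratory, and no primary or secondary endpoint, sample size or safety analysis is affected.

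**What to change.** In 8.2 and 8.4, replace the reference to prognostic and predictive value with *association with outcome in pembrolizumab-treated patients*, which matches 1.4.1 and the introduction to Section 8. Add that these associations cannot distinguish prognostic from predictive value.

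In 12.2.6.3, add: *Effect modification will be explored only for the pre-surgical dose, by a marker-by-group term in a Cox model in the randomised Stage 1 patients, and only for markers measured before Group A's first dose (archived tissue, pre-treatment blood). It will be reported as an estimate with 95% CI. No claim of predictive value for pembrolizumab itself will be made.*

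The cost is a few sentences and one model term; the pre-dose samples are already collected. The claim becomes narrower, and the added analysis does not reach the markers measured on protocol-surgery tumour. Its estimate will be imprecise: about 33% power with 15 v 15 even for assumed hazard ratios per SD of 2.0 in A and 1.0 in B. Adding the Stage 2 patients would raise that to about 48%, but they are not randomised.
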